# **10.0 Data and Specimen Banking\***

- 10.1 Data banking will be performed at the conclusion of this study in order to use for research or post-hoc power analysis. The repository will consist of the digital data collected during the study. Data will be stored for a period of three years, and may only be accessed via password through the computer in the Motion Analysis Laboratory. Only the PI will have access to this data, and will only use the data with additional IRB approval of a new protocol. Anyone else wishing to use the data must first ask the PI permission before initiating a new protocol.
- 10.2 Data to be stored is the raw digital data (kinetic and kinematic) and analyzed (T1) collected during motion analysis.
- 10.3 The PI, or another researcher after first asking permission of the PI, will have to submit an application to the IRB before using the stored data for any research purposes. After IRB approval of a new protocol, the password for the computer will be provided, and the researcher will have access to the raw data only. They will be responsible for any analysis that may be required for new variables.

# **11.0** Data Management\* and Confidentiality

- 11.1 The three trials without and with TA contraction during ambulation will be analyzed to determine  $T_1$  for each trial. The average of the three trials under each condition will be calculated. Statistical analysis will include a repeated measures, two mean comparison (a paired-samples t-test or Wilcoxon signed rank depending on results of assumption analysis). Statistical analysis will be performed using the most up to date version of SPSS available to the PI.
- 11.2 The study is serving as a pilot study for post-hoc power analyses of the variables under consideration for future study.
- 11.3 The computer, which stores and analyses the raw kinetic data, is password protected. Only the PI and the faculty member in charge of the lab have the password. In addition, only the faculty of the SAHP has access to the lab via key entry. All participants will be given a code-identifier, with a key kept in the compliance binder for the study (also containing informed consent documentation). This compliance binder will stay in the PI's office in a locked drawer.
- 11.4 Once the raw data is saved on the computer, the files will be backed up on a flash drive which will also be kept in a locked drawer in the PI's office.
- 11.5
- Data will be stored on the computer in the motion lab, and analyzed data will be backed up on a flash drive locked and stored in the PI's office drawer.
- Data will be stored for three years per the data banking procedure noted in section 10.1-10.3.
  - See 10.1-10.3 for persons having access to the data.

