# 1.0 Objectives\*

1.1 The purpose of this study is to study the effects of core activation on knee joint loading during ambulation in patients with knee osteoarthritis (OA). This study aims to investigate the effects of transversus abdominis (TA) activation during simultaneous kinetic analysis of time to initial peak ground reaction force (T1) at the heel in the sagittal plane.

The objective of this study is to determine whether patients with knee OA demonstrate changes in  $T_1$  during comfortable gait speeds when actively contracting the TA muscle. In addition, this study will serve as a pilot study in order to perform a post-hoc power analysis for future study on the effects of the independent variable (TA contraction/changes in core stability) on the dependent variable ( $T_1$ ).

1.2 Null hypothesis: There will be no change in  $T_1$  in patients with knee OA during gait while contracting their TA.

Alternate hypothesis: There will be a decrease in  $T_1$  in patients with knee OA during gait while contracting their TA.

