spine to ipsilateral medial malleolus bilaterally (cm) via tape measure, and knee and ankle joint widths (cm) via a caliper. After collection of this data is completed and recorded, the PI will place reflective markers on the patient's skin via adhesive tape made for this purpose at the following landmarks bilaterally: ASIS, posterior superior iliac spine, lateral thigh, knee center of rotation, lateral leg, heel, lateral malleolus, and base of the second metatarsal. When this set-up is complete, static calibration of the motion analysis system will take place with the participant standing still in the capture area. When this is complete, the participant will be allowed a 2-minute warm-up by walking back and forth in the capture area. When this is completed the participant will be asked to walk at a comfortable pace across the capture area. Three trials with good force plate contact will be collected. After these three trials are obtained, the patient will lie supine on the mat in the lab, and will be taught how to perform a TA contraction. A Pathway MR-20 biofeedback device (The Prometheus Group, Dover, NH, USA) with two electrodes will be placed just medial to the ASISs on the participant's abdomen. A baseline maximal contraction will be performed supine, and the amplitude of contraction will be considered maximal voluntary isometric contraction (MVIC). The device will be set to provide audible feedback at 50% MVIC. The task will be repeated seated, standing, then ambulating three practice trials on the capture area. The participant will then be instructed to perform an additional three comfortable paced ambulation trials with good force plate contact while contracting the TA enough to cause audible feedback via the biofeedback device. After completing these three trials, the biofeedback device and reflective markers will be removed, and the participant will have completed their active participation in the study.

Procedure/Test	Rate of Occurrence
Anthropometric Data Collection	1
Reflective Marker Placement	1
Biofeedback Placement	1
TA Contraction Trials with	At least once per body
Biofeedback	position
Walking Trials without TA	2
Contraction	3
Walking Trials with TA Contraction	3

Q	3	
/		

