#### 20.0 Resources Available

- 20.1 The PI is a licensed physical therapist specializing in orthopaedics. The PI has training in motion analysis. A professor from another physical therapy at Texas Woman's University (TWU) in Houston will be present to assist with working the Vicon System in order to facilitate data collection and train the PI on data analysis of the raw data. The visiting professor is a tenure associate professor at TWU who has published in the area of motion analysis in PT in the past.
- 20.2
- The Rehabilitation Faculty Practice Clinic treats many patients with knee OA, and has treated many in the past. There are dozens of potential applicants the PI has access to through the clinic. It is more feasible to recruit this small sample size in a short period of time due to the nature of this particular study.
- The PI has a faculty contract which allows for 30% effort towards research/scholarship. During the time this study is ongoing, 2/3 of this time will be devoted completely to this project.
- The Motion Analysis Laboratory is located on the second floor (room 2-217) in the SAHP. The lab is 700 square feet, and has a Vicon Vero 2.2 (8 camera) motion analysis system with 2 AMTI force plates embedded in the raised platform (8 x 24 ft). There are two desktop monitors connected to the computers used for data collection and analysis for viewing of output and processing.
- The PI is the author of the protocol, and the only full-time investigator.

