### 24.0 Provisions to Protect the Privacy Interests of Subjects

- 24.1 The participants will only interact with the PI directly during both the informed consent process and in data collection. The visiting professor who will be working the motion system will be present in the room during data collection; however, the PI will be performing all instruction, data collection, and leading the investigation.
- 24.2 The PI will have already met all the participants during informed consent, and may even be familiar with him from their time receiving treatment in the clinic. In addition, the lab is located two floors above the clinic, and is a private setting, so there is a reduced risk of them being observed by anyone not participating in the research.
- 24.3 The PI is able to access any information at any time since he is protecting all the hardcopy and digital data. No one else will be able to access the information.

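### Walks are accepted on an undefined contact criterion, and T1 appears to be derived unmasked by the PI who predicts its decrease: an avoidable, probably modest, route to bias

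*Protocol*

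**What the plan says.** All references are to the protocol.

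- **Hypothesis.** Section 1.2 is directional: "Alternate hypothesis: There will be a decrease in" T1 with transversus abdominis (TA) contraction. Section 20.2 adds: "The PI is the author of the protocol, and the only full-time investigator".
- **Who collects.** Section 24.1: "the PI will be performing all instruction, data collection, and leading the investigation". A visiting professor operates the motion system in the same room.
- **Which walks count.** Section 9.2, control condition: "Three trials with good force plate contact will be collected". The TA condition then requires an "additional three comfortable paced ambulation trials with good force plate contact". Neither place says what makes contact good, how many attempts are allowed, or what happens to the record of a rejected walk.
- **Whether the condition is known.** Control walks always come first, and TA walks are performed "while contracting the TA enough to cause audible feedback via the biofeedback device". Everyone in the room knows the condition.
- **Who derives T1.** Section 11.1: "The three trials without and with TA contraction during ambulation will be analyzed to determine" T1 for each trial; the three values per condition are then averaged and compared by a paired t-test or Wilcoxon signed rank test. No analyst is named. Section 20.1 says the visiting professor is there to "facilitate data collection and train the PI on data analysis of the raw data", and section 7.1 makes timely completion of the primary analysis the PI's own goal.
- **Coding.** Section 11.3 gives each participant a code for confidentiality. It does not hide the condition.

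**The concern.** Two steps lie between the walk and the analysed number: deciding that a walk is usable, and extracting T1 from the force record. The protocol gives the first to someone who knows the condition and expects a particular result, on an undefined criterion. It appears to give the second to the same person, with no masking provided for.

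A tendency to accept walks or settle T1 values more readily in the predicted direction would enter the paired difference directly. Such a shift is systematic, so it would not average out at any sample size. It matters here because sections 1.1, 9.1 and 11.2 give the study one quantitative use: a post-hoc power analysis for a later study. An effect biased in the predicted direction would make that study too small.

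**Working it through.** The protocol states no SD, effect size, alpha or power, so there is no figure to reproduce. The check has two parts.

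**1. Stated, inferred or absent**

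| Link in the chain | Status |
|---|---|
| PI predicts a decrease | Stated (1.2, 20.2) |
| PI instructs and collects in both conditions | Stated (24.1) |
| Condition known during walks | Follows from 9.2 |
| Contact criterion undefined | True of the protocol as shown (9.2) |
| PI derives T1 | Inferred (7.1, 20.1); 11.1 names nobody |
| T1 files masked to condition | Not provided for; only participant codes (11.3) |
| T1 read by eye | Not stated |
| T1 visible when a walk is accepted | Not stated |
| More good walks collected than are kept | Not stated; three per condition (9.2) |

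The first four rows and the sixth are enough to show an unprotected route. The last three are what a large bias would need, and the protocol supports none of them.

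**2. A hypothetical ceiling**

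Assumptions, none from the documents: T1 varies normally from walk to walk with the same SD in both conditions (unit: one trial SD); there is no true effect; one or two surplus TA walks exist; and the three shortest T1 values are kept.

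- Four walks: expected normal order statistics are -1.029, -0.297, 0.297, 1.029. Mean of the lowest three = (-1.029 - 0.297 + 0.297)/3 = **-0.34**.
- Five walks: -1.163, -0.495, 0, 0.495, 1.163. Mean of the lowest three = (-1.163 - 0.495 + 0)/3 = **-0.55**.

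The yardstick is the standard error of the mean paired difference, not that of one person's three-walk mean (1/√3 = 0.58). If the condition effect does not vary between people, it is √(2/3)/√n: 0.47 for n = 3 and 0.37 for n = 5 (section 23.1 plans three to five participants). The extreme shifts are then between 0.34/0.47 = 0.7 and 0.55/0.37 = 1.5 standard errors.

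Simulated two-sided type I error of the paired t-test (nominal 0.05 assumed, 100,000 runs per case), with the three shortest of four TA walks kept and control walks unselected:

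| SD of condition effect between people | n = 3 | n = 5 |
|---|---|---|
| 0 | 0.075 | 0.12 |
| 1 trial SD | 0.060 | 0.076 |

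Selecting three of four in opposite directions in both conditions doubles the shift to about -0.69. With no between-person variation, the error is then 0.16 (n = 3) or 0.35 (n = 5).

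For the extraction step, a constant shift of 0.25 trial SD in TA walks alone gives 0.063 (n = 3) or 0.084 (n = 5), again with no between-person variation.

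With the first three usable walks kept and T1 extracted blind, the simulated bias is zero and the error about 0.05.

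The error rates concern the t-test only. With five pairs the smallest two-sided Wilcoxon p-value is 2/2⁵ = 0.0625, so that test cannot reject at 0.05. The biased estimate is the main issue.

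**The case against.** The strongest reply is that the serious version of this problem is not in the document. A reader might infer that the PI picks the initial peak by eye, or repeats walks until short T1 values appear. The text supports neither:

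- Section 11.3 speaks of a computer that stores and analyses the kinetic data, and no place describes manual reading.
- Acceptance turns on plate contact during the session, and nothing says that T1 is available then. Three good walks per condition are collected, not a surplus to choose from.
- The visiting professor is present and operating the system.

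This stands, and it is why the selection figures cannot be read as estimates for this trial.

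Three further points also stand. Section 20.1 says the PI has motion analysis training, so inexperience should not be inferred. Section 9.3 refers to a data-collection worksheet that is not shown; it may record rejected walks, so the absence of a log cannot be asserted. The algorithm for locating the peak, and masked extraction, could be set out in an analysis plan that is not shown.

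The reply does not dispose of walk acceptance. That is a laboratory procedure which section 9.2 itself sets, on an undefined criterion applied by an unmasked person with a directional hypothesis. An analysis plan written afterwards cannot recover walks that were not recorded. Nor does instrumented measurement remove the case for masking, though it probably makes extraction bias smaller than for a subjective outcome.

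**Conclusion.** The point holds as a cheap improvement. The protocol leaves an avoidable route to bias in the T1 difference, mainly through undefined walk acceptance and secondarily through T1 extraction not masked to condition. That the PI performs the extraction is a well-supported inference, not a statement in section 11.1.

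The size cannot be estimated from the documents and is probably modest. The shifts of 0.34 and 0.55 trial SDs are ceilings for one or two surplus TA walks under perfect selection on T1, which lies outside the written procedure. It would be wrong to conclude that the T1 difference is biased, or that bias is as large as the noise. The conclusion is that the route is open, that it leads into the power analysis for the next study, and that closing it costs little.

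**What to change.** **Section 9.2.** Before collection starts, define acceptable contact objectively, for example the whole foot inside one plate with the other foot off it. Keep the first three walks per condition that meet the rule. Record every rejected walk with its reason before T1 is computed; if the worksheet already does this, say so.

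**Section 11.1.** Derive T1 by one fixed rule applied identically to every trace, from files coded without condition. Open the key only after all T1 values are locked. State who performs the derivation and who holds the key.

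**Cost.** File recoding and a fixed script or software setting, with no added participant time. If someone other than the PI holds the key, the access provisions in sections 10.1 to 10.3, 11.3 and 24.3 need a small wording change. The visiting professor is one candidate, but comes from another institution, and enrolment and analysis together are planned to take about eight months, so availability needs checking. The PI gives up any look at results by condition until T1 is locked. Participant and coach remain unmasked, so the effect of coaching on the walks themselves is not removed.

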#### 9.0 Procedures Involved\*

- 9.1 This project serves as pilot study for future investigation on the role of core stabilization on gait kinetics in patients with knee OA. Therefore the sample size will be small. Post-hoc power analysis will inform the PI about requirements for participant recruitment needs for future investigations.
- 9.2 After informed consent is completed, participants will be scheduled for a session in the Motion Analysis Laboratory in the SAHP. Patients will have already been asked to wear close fitting, exercise appropriate clothing to allow marker placement, and prevent marker blocking during motion analysis. Data collection will begin by collecting the following anthropometric data: body weight (pounds, converted to kilograms) via a scale, height (inches, converted to mm) via a tape measure, leg length from ipsilateral anterior superior iliac

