# 13.0 Withdrawal of Subjects\*

- 13.1 The PI does not anticipate any circumstances where a participant may wish to withdraw since this study only requires a very shortterm in-person participation. However, if after data collection a participant contacts the PI wishing to not be included in any data analysis/publication, their data will be withdrawn from analysis.
- 13.2 As soon as a participant informs the PI they wish to withdraw, a notation will be made in the compliance binder, and their data will not be analyzed upon data analysis.

13.3 Due to the brief nature of participation and data collection, anyone who withdrawals from the study cannot be used for data analysis.

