### 23.0 Local Number of Subjects

23.1 Three to five participants will be recruited for the purposes of this pilot study.

23.2 NA

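### Section 11.1 lets an assumption check switch the only hypothesis test to Wilcoxon signed-rank, whose exact version cannot reach 0.05 with 3 or 4 participants, and with 5 only one-sided if all five decrease

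*Protocol*

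**What the plan says.** Section 1.2 sets a formal null of no change in T1 and a directional alternative ("Alternate hypothesis: There will be a decrease in" T1 during TA contraction). Section 11.1 gives the only test of it. Three walking trials are taken with and three without TA contraction, and "The average of the three trials under each condition will be calculated". The two conditions are then compared by "a paired-samples t-test or Wilcoxon signed rank depending on results of assumption analysis". The protocol does not name the check, alpha, the sidedness of the test, or whether the p-value is exact or large-sample. On software it says only: "Statistical analysis will be performed using the most up to date version of SPSS available to the PI".

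Section 23.1 fixes the size: "Three to five participants will be recruited for the purposes of this pilot study". Section 9.1 presents this as deliberate in a pilot: "Therefore the sample size will be small". Under section 13.3, "anyone who withdrawals from the study cannot be used for data analysis", so the analysed number can be lower than the number recruited.

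**The concern.** A signed-rank test on n pairs has only 2^n equally likely sign patterns under the null, so its p-value has a floor that depends on n alone. With 3 to 5 pairs that floor lies above 0.05 in nearly every case. The rule in section 11.1 can therefore send the study's one hypothesis test into a branch where rejection is impossible. A non-significant result there would say nothing about TA contraction, yet could be read as a negative finding.

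Two features add to this. First, the decision to switch rests on a check of 3 to 5 values, which can hardly detect non-normality. Second, the exact and large-sample p-values can fall on opposite sides of 0.05, so the same data could be called significant or not depending on a setting that the protocol leaves open.

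**Working it through.** **Inputs.** n = 3, 4 or 5 pairs (sections 23.1 and 11.1; one averaged value per participant per condition, one limb each assumed). The alternative is a decrease (section 1.2). Assumed, because the protocol does not give them: alpha 0.05; Shapiro-Wilk at 0.05 as the check; a mean/SD of the paired differences from 0.5 to 2. The protocol has no derived figure to reproduce.

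**1. Smallest attainable Wilcoxon p-value** (no ties, no zero differences). The most extreme result, all differences in one direction, has exact p = 1/2^n one-sided and 2/2^n two-sided. The large-sample version without continuity correction uses z = [n(n+1)/4] / √[n(n+1)(2n+1)/24]:

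- n = 3: 3/√3.5 = 1.604
- n = 4: 5/√7.5 = 1.826
- n = 5: 7.5/√13.75 = 2.023

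| n | Exact one-sided | Exact two-sided | Large-sample one-sided | Large-sample two-sided |
|---|---|---|---|---|
| 3 | 1/8 = 0.125 | 2/8 = 0.25 | 0.054 | 0.109 |
| 4 | 1/16 = 0.0625 | 2/16 = 0.125 | 0.034 | 0.068 |
| 5 | 1/32 = 0.031 | 2/32 = 0.0625 | 0.022 | 0.043 |

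The only exact entry below 0.05 is one-sided at n = 5. The next possible one-sided value there is 2/32 = 0.0625, so all five participants must decrease. One withdrawal from five gives n = 4 and closes that route. Exact and large-sample values straddle 0.05 one-sided at n = 4 (0.0625 against 0.034) and two-sided at n = 5 (0.0625 against 0.043). Two-sided at n = 3 and n = 4, neither version can reach 0.05.

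**2. The paired t-test has no such floor.** It reaches two-sided 0.05 when |mean|/SD exceeds t(0.975, n−1)/√n, which is 2.48, 1.59 and 1.24 at n = 3, 4 and 5.

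**3. How often the check triggers** (Shapiro-Wilk at 0.05, simulation):

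| Distribution of differences | n = 3 | n = 4 | n = 5 |
|---|---|---|---|
| Normal | about 5% | about 5% | about 5% |
| Exponential | 7% | 12% | 16% |
| Lognormal | 8% | 17% | 24% |

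Most skewed samples pass, and about 1 in 20 normal samples is sent to Wilcoxon.

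**4. Overall cost for normal differences**, always-t against the switch with exact Wilcoxon, two-sided:

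| Mean/SD | n = 3 | n = 4 | n = 5 |
|---|---|---|---|
| 1 | 0.18 vs 0.17 | 0.29 vs 0.27 | 0.40 vs 0.38 |
| 2 | 0.47 vs 0.45 | 0.75 vs 0.71 | 0.91 vs 0.86 |

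At a mean/SD of 0.5 the two-sided loss is under 1 point. One-sided at a mean/SD of 2, the loss is about 5 points at n = 4 (0.91 vs 0.86) and under 1 point at n = 5 (0.973 vs 0.968). One-sided at n = 4 and a mean/SD of 1, it is about 2.4 points (0.462 vs 0.438).

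**The case against.** The study is openly a small pilot, and the t-test branch will be used for most samples. With normal differences the Wilcoxon branch is entered only about 5% of the time, so the overall loss is small and the larger figures need a very large effect. That is correct, and it limits the severity.

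The impossibility also depends partly on the exact test. With large-sample p-values the switch costs almost nothing at a mean/SD of 2: 0.909 vs 0.908 one-sided at n = 4, and 0.913 vs 0.910 two-sided at n = 5. An analysis plan could settle exact or large-sample, alpha, sidedness and the check. But the large-sample version crosses 0.05 only by understating the exact p-value, and the two-sided floors at n = 3 and 4 stay above 0.05 under either version. The data-driven rule is fixed in the protocol itself, and no later detail makes the exact branch informative at n = 3 or 4.

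Always using the t-test is not free either. With zero-mean exponential differences it rejects about 11–12% of the time two-sided, against 10–11% with the switch. With the skew in the unfavourable direction the one-sided rates are about 16% and 15%. The difference of about 1 point is real but small, because the check misses most skewed samples anyway.

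Finally, the mean and SD of the differences can be computed whichever test is run, and section 13.1 expects no withdrawals from a single session. Both points stand in part. Section 11.1 does not commit to reporting the mean and SD that the next study needs, and the withdrawal remark matters only inside the exact Wilcoxon branch at n = 5.

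**Conclusion.** The point holds and should be fixed, although it is not a fatal flaw. At a conventional 0.05, the exact form of the fallback test cannot reject at n = 3 or 4 in either direction, nor two-sided at n = 5. The one remaining case, one-sided at n = 5, needs all five participants to decrease. These floors are exact and need no assumed effect size or SD. They rest on alpha 0.05, one independent difference per participant, and the exact p-value.

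The trigger rates and power figures also rest on Shapiro-Wilk as the check, and the power comparisons on normal differences. On those terms the overall loss is modest, reaching about 5 points only at a mean/SD of 2. The main harm is to interpretation: in the exact branch at n = 3 or 4, a non-significant result is fixed before any participant is measured.

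**What to change.** Replace the bracketed rule in section 11.1 with:

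> The analysis is the mean within-participant difference in T1 (TA minus no TA) with its t-based 95% confidence interval (n−1 df) and a paired t-test, used regardless of any assumption check; each participant's two averages are shown.

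If Wilcoxon is kept as a sensitivity analysis, add:

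> The exact p-value is reported together with the smallest p-value attainable at the analysed n.

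This is one or two sentences and needs no new data. The costs should be acknowledged. The t-interval relies on normality that 3 to 5 values cannot verify. It will also be wide, with a half-width of t(0.975, n−1)/√n = 2.48, 1.59 or 1.24 SDs of the differences at n = 3, 4 or 5. The change does not cure the low power that comes from the sample size.
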